CLINICAL STUDY PROTOCOL

Title: Preventive Effects of Ginseng against Atherosclerosis and Subsequent ischemic Stroke:

A randomized controlled trial

(PEGASUS)

Study Type: Single-center, Randomized, Double-blind, Placebo-controlled trial; Investigator-initiated trial

Protocol Number: KGC2026-26

NCT Number: NCT02796664

Version of the document: 6.3, Final version

Date of the document: March 02, 2018

1. Ethical considerations

This trial will be conducted in compliance with Good Clinical Practice (GCP) and Declaration of Helsinki. This trial will start after the written approval of the institutional review board (IRB) of our institution is obtained.

2. Introduction or background information

Atherosclerotic stenosis in a cerebral artery progressing more than 70% caused cerebral ischemia, leading to developing collateral circulation. Ischemic symptoms of a patient are varying by the development of collateral circulation, which is caused by not only anatomical differences but also angiogenesis factors. Recent study reported that Korean red ginseng (KRG) had a good effect on cardiovascular system by affecting nitric oxide (NO). Endothelial nitric oxide synthase (eNOS) was studied a lot because that NO produced by eNOS was associated with anti-inflammation and anti-atherosclerosis. Moreover, KRG was reported that it had a vasodilation effect, a blood pressure stabilizing effect and an anti-platelet effect such as reducing platelet aggregation. Several effects mentioned above suggests that KRG had the preventive effect in cardiovascular system and ischemic cerebral stroke.

Therefore, we hypothesize that ginseng has prevention effects against atherosclerosis and subsequent ischemic stroke. The preventive effects of ginseng on cerebral ischemic stroke will be evaluated in the group of the patients with advanced atherosclerosis such as severe stenosis or occlusion in the intracranial arteries. In addition, the changes of collateral perfusion state on an ischemic territory caused by atherosclerosis will be evaluated using

quantitative magnetic resonance angiography as a surrogate marker.

3. Literature review

- A. Some reports showed that ginseng had a good effect on cardiovascular system through affecting NO.
- B. It was reported that NO produced by endothelial nitric oxide synthase (eNOS) was related to anti-inflammation and anti-atherosclerosis.
- C. Ginseng had effects of reducing platelet aggregation, lowering mean systolic pressure, and vasodilatation.

4. Study objectives and purpose

The aim of this trial is to study prevention effects of ginseng against atherosclerosis and subsequent cerebral ischemic stroke in high-risk patients with severe steno-occlusive lesions in internal carotid artery, middle cerebral artery, and posterior circulation.

5. Expected study duration

From the date of institutional review board (IRB) approval to July 31, 2018.

6. Study subjects

A. Selection criteria

1) Inclusion criteria

- i. Aged between 20 and 80.
- ii. Severe stenosis or occlusion at an internal carotid artery, middle cerebral artery and vertebrobasilar system in cerebral angiography.
- iii. Any stroke risk factors such as hypertension, diabetes, hyperlipidemia, smoking and alcohol drinking.
- iv. No adverse effect history of ginseng administration.

2) Exclusion criteria

- i. Genetic cerebrovascular diseases.
- ii. Adverse reaction to contrast medium.
- iii. Pregnant women.
- iv. History of previous intra-arterial thrombolysis, cerebral angioplasty and/or stenting, carotid endarterectomy, and bypass surgery.
- v. History of cardioembolic stroke or possibility of cardioembolic stroke.
- vi. Possibility of cancer stroke.
- vii. Renal failure (GFR < 30 ml/min) or liver disease.

B. Risk and benefit evaluation

- 1) Potential risk of this study: Although additional risks are considered as minimal, potential risks participating in this trial are showed as follows: any adverse effects related to ginseng; pain, bruise or hematoma at puncture site, dizziness, syncope, or infection related to cerebral catheter angiography.
- 2) Potential benefit of this study: Although there would be no potential benefit for

participants, their participations in this trial would help medical advancements.

- 3) Conclusion of risk and benefit analysis: It is considered that a potential benefit would be bigger than a potential risk because of less adverse effect of ginseng on subjects, and an important suggestion to future treatment.

C. Eligible patients

Any inpatients or outpatients who are referred to the department of radiology for transfemoral cerebral angiography will become eligible patients. Among them fulfilled selection criteria, investigators will obtain written informed consent individually.

7. Study design

A. Type of a trial design

A single-center, double-blind, parallel-group, placebo-controlled randomized trial.

B. Outcomes

1) Primary outcome:

- i. Presence of ischemic stroke or TIA (Transient Ischemic Attacks) assessed by symptom history during one-year follow-up and measured by number of patients in each group.
- ii. Presence of other cerebro-cardiovascular morbidity or mortality assessed by aggravation of patient status (mRS, modified Rankin Scale) at out-patient clinic during one-year follow-up and measured by the number of patients.

2) Secondary outcome:

- i. Changes in volumetric blood flow (ml/Sec) in quantitative MRA measured

by percentage change from the baseline study.

- ii. Changes in velocity (cm/Sec) in quantitative MRA measured by percentage change from the baseline study.
- iii. New FLAIR MR lesions assessed on one-year follow-up MRI and measured by the number of patients.

C. Sample size calculation

Assuming the proportion of 0.1 in the ginseng group and the proportion of 0.4 in placebo group in the analyses of primary and secondary outcomes, calculated sample size would be 29 patients each group for determining difference between two groups in the level of alpha of 0.05, power of 0.8 and 1:1 sampling ratio (equality test).

D. Randomization and follow-up of outcomes

There are two study groups as follows: a ginseng group as an intervention group, a promising placebo group as a control group. The participants will be randomly allocated to either the ginseng group or the placebo group by 1:1 ratio according to random permuted block with a block size of 20. Both groups will be followed up at 1, 3, 6 and 12 months after randomization. At each follow-up, history of the primary outcome, any adverse effects, any co-administration drugs, and study drug compliance will be evaluated. The secondary outcomes will be evaluated by comparison of the results of quantitative MR angiography studies performed at baseline and 12 months after randomization.

E. Study drugs and administration

Two study drugs are identical in appearance. In the intervention group, 2-gram ginseng per day (0.5 grams/capsule, 2 capsules twice a day) will be administrated for

12 months. In the control group, 2-gram placebo per day (0.5 grams/capsule, 2 capsules twice a day) will be administrated for 12 months.

F. Safety evaluation and reporting

If any adverse effects are occurred, the participants will report the problem to an investigator. The investigator will appoint outpatient clinic. When the subject visits the outpatient clinic, the investigator will evaluate allergic symptoms such as redness, swelling, respiratory difficulty and grade the symptom severity. The investigator will gather other subject symptoms as patient says.

G. Primary outcome evaluation

The presence of any cerebral ischemic symptoms is the primary outcome. The history of cerebral ischemic symptoms includes transient ischemic attack (TIA) and cerebral ischemic infarction. If the related history is reported, a diffusion-weight MRI will be performed. It will be evaluated whether new ischemic lesion is related to the steno-occlusive lesion confirmed by cerebral angiography at baseline.

H. Secondary outcome evaluation

A quantitative MR angiography (QMRA) with noninvasive optimal vessel analysis (NOVA) will be performed for evaluating secondary outcomes at baseline and 12 months after randomization. QMRA with NOVA will measure blood flow at the predetermined sites. The results would become an indirect measurement of collateral flow state of a steno-occlusive vascular lesion.

8. Data collection forms and items

Subject No.	Sex	Age	Results of cerebral catheter angiography			The presence of acute ischemic lesions
			The presence of a steno-occlusive lesion at internal carotid artery, middle cerebral artery, and vertebrobasilar system	Stenosis severity (Severe/moderate/mild)	Complete total occlusion	

Medication Information				
Duration (mo)	Dose	Date Start	Date End	Compliance

※ Compliance

Drug name	Expected administration days	Actual administration days	Compliance (%)
Ginseng			
Placebo			

Non-invasive Optimal Vessel Analysis (NOVA) (at baseline)	Non-invasive Optimal Vessel Analysis (NOVA) (at 12 months after randomization)

Brain-MRI (New lesions on FLAIR) (at baseline)	Brain-MRI (New lesions on FLAIR) (at 12 months after randomization)

The presence of any ischemic stroke history at 3 months follow-up	The presence of any ischemic stroke history at 6 months follow-up	The presence of any ischemic stroke history at 9 months follow-up	The presence of any ischemic stroke history at 12 months follow-up

The follow-ups can be conducted in outpatient clinics or by telephone interview performed by experienced nurses since the presence of ischemic stroke or TIA history is asked, and mRS is evaluated in the interview. The investigators can do neurologic evaluations if needed.

9. Blood laboratory test and imaging test

A. Blood laboratory test

none

B. Imaging test

- 1) A quantitative MR angiography (QMRA) with noninvasive optimal vessel analysis (NOVA) for the changes of cerebral blood flow.
- 2) A brain MRI including FLAIR for the presence of new cerebral ischemic lesions.

10. Subject discontinuation (Drop-out)

- 1) Difficulty in administration of study drugs.
- 2) Impossible to follow up.

11. Patient data safety

Any identifiable human material and data will be excluded in the research. And a subject will be given a subject number. Collected data will be managed with a password by only the principle investigator and investigators. The data will be discarded after 3-year mandatory storage period.

12. Audit

The principle investigator will carry out inspections at finishing data collection and at

finishing data analysis.

13. Statistical analysis

The results will be analyzed in intention-to-treat method. For analysis of primary outcome, Fisher's exact test will be used for a dichotomized variable.

14. Detailed study schedule

Visits	Screening baseline	1 st F/U (Telephone/ OPD visit)	2 nd F/U (Telephone/ OPD visit)	3 rd F/U (Telephone/ OPD visit)	4 th F/U (Telephone/ OPD visit)
Date	0 day	1 month (± 2 weeks)	3 months (± 2 weeks)	6 months (± 2 weeks)	12 months (± 2 weeks)
Obtaining consent	●				
MR	●				●
Drug compliance		●	●	●	●

15. References

4) Lee CH, Kim J-H. A review on the medicinal potentials of ginseng and ginsenosides on cardiovascular diseases. *J Ginseng Res.* 2014;38:161-166

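### Current ginseng users can be enrolled in either arm, and non-study ginseng is neither addressed nor specifically recorded, so outside use could dilute the placebo contrast

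*Combined protocol and SAP*

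**What the plan says.** Section 6.A lists four inclusion and seven exclusion criteria. One concerns ginseng, inclusion iv: "No adverse effect history of ginseng administration". No exclusion covers current or recent use, and there is no washout.

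Section 7.E gives each arm its assigned capsules for 12 months and does not mention ginseng from other sources. Section 10 gives two reasons for drop-out, and outside ginseng is not one of them.

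Section 7.D states "Both groups will be followed up at 1, 3, 6 and 12 months after randomization", and that at each of these contacts "any adverse effects, any co-administration drugs, and study drug compliance will be evaluated", along with the history of the primary outcome. The section 8 forms hold a general medication table (duration, dose, dates, compliance) without a column for the product name, and a compliance table for the two assigned products. The section 14 schedule shows consent, MR and drug compliance, but no co-medication item.

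The sample size in section 7.C rests on this contrast: "Assuming the proportion of 0.1 in the ginseng group and the proportion of 0.4 in placebo group". Section 13 plans an intention-to-treat analysis.

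**The concern.** The trial compares ginseng with no ginseng. A placebo patient who takes ginseng from another source receives the agent under test but is counted as a control. If ginseng lowers event risk as the protocol hypothesises, each such patient moves the placebo event rate toward the ginseng rate. Intention-to-treat, which is the right primary analysis, keeps that dilution in the estimate.

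The plan did consider prior ginseng exposure, because it wrote a criterion about it. That criterion removes people who reacted badly and lets through those who tolerate ginseng and may still be taking it.

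The flow and velocity outcomes in section 7.B are affected by a different route. They are percentage changes from baseline, so in a current user, in either arm, the baseline scan is already taken under exposure.

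At stake is how a null result would be read. Unless outside use is recorded by arm, the trial would have limited means of judging whether contamination contributed.

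**Working it through.** **Inputs from section 7.C.** Event proportions 0.1 (ginseng) and 0.4 (placebo), with "in the level of alpha of 0.05, power of 0.8 and 1:1 sampling ratio (equality test". Sidedness is not stated; I read the equality test as two-sided. The result given is "calculated sample size would be 29 patients each group".

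**Step 1: reproduce the plan's figure.** Unpooled two-proportion formula:

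n = [p1(1 − p1) + p2(1 − p2)] × (1.960 + 0.842)² / (p2 − p1)² = (0.09 + 0.24) × 7.849 / 0.09 = 28.78, rounded up to 29.

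This matches. Power at 29 per group is Φ(0.3 / √(0.33/29) − 1.960) = Φ(0.852) = 0.803, so the design has no reserve for dilution.

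**Step 2: add contamination.** Let c be the share of placebo patients taking outside ginseng with the full planned effect. The documents give no value for c, so a range is shown. The placebo rate becomes 0.4(1 − c) + 0.1c = 0.4 − 0.3c. The ginseng rate is held at 0.1.

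| c (assumed) | Placebo rate | Power at 29 per group | n per group for 0.80 power |
|---|---|---|---|
| 0 | 0.40 | 0.803 | 29 |
| 10% | 0.37 | 0.725 | 35 |
| 20% | 0.34 | 0.635 | 43 |
| 30% | 0.31 | 0.536 | 55 |

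Example for c = 20%: the variance term is 0.09 + 0.34 × 0.66 = 0.3144, and power is Φ(0.24 / √(0.3144/29) − 1.960) = Φ(0.345) = 0.635.

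**Step 3: relax the full-effect assumption.** If outside ginseng had half the planned effect, the placebo rate would be 0.4 − 0.15c. Power at c = 10%, 20% and 30% would then be 0.766, 0.725 and 0.681.

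**Step 4: the planned test.** Exact power of Fisher's test (section 13) at 29 per group is 0.681 with no contamination, and 0.588, 0.487 and 0.385 at 10%, 20% and 30%. The gap between 0.803 and 0.681 comes from sizing with one test and analysing with another. It is a separate matter. Only the further fall from 0.681 belongs to this point.

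**The case against.** A reader might infer that outside ginseng is never asked about. The documents do not support that. Section 7.D evaluates co-administered drugs at 1, 3, 6 and 12 months, and the protocol's own vocabulary treats ginseng as a drug: 7.E calls both products study drugs, and the section 8 compliance table lists ginseng in its drug-name column. An investigator could well record outside ginseng under that question. What stands is narrower: ginseng and supplements are not named, a patient may not count a food or supplement as a drug, baseline use is not covered, and the forms give the answer no clear place. The form gap is not special to ginseng, since section 8 has no dedicated field for adverse effects or mRS either.

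A reader might also infer that inclusion iv shows the sponsor expects users to enrol. It is a tolerability screen; it admits users but does not predict how many.

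Nor do the documents support a claim that every outcome is biased toward no difference. For flow and velocity the exposed baseline works differently. A placebo patient who stopped ginseng after the baseline scan could even widen the contrast. No calculation from the documents settles the direction.

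The size is hypothetical. Self-chosen use at unknown dose and duration need not have the full effect. The source of the 0.4 is not given, and if it already reflects background use, subtracting for contamination counts it twice.

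Finally, one can argue that background use only changes the question, to the effect of adding study ginseng to usual habits. That is a legitimate target, but the protocol does not state it.

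These objections limit the wording and the size. They do not change the fact that the plan, followed exactly, admits placebo patients who are taking the study agent.

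**Conclusion.** The point holds in this form: current users are eligible for either arm, non-study ginseng is not addressed, and its use is not specifically recorded at baseline or follow-up. If ginseng works as hypothesised, use in the placebo arm biases the event comparison toward the null.

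On the plan's own formula, power at 29 per group would fall from 0.80 to 0.73, 0.64 and 0.54 at 10%, 20% and 30% use. These figures assume the full planned effect in placebo users, an unchanged ginseng-arm rate, and that 0.4 describes placebo patients not taking ginseng. With the full effect assumed, each is an upper bound on the loss at that usage rate. The actual rate is unknown, so this is a documented gap that is cheap to close, not a demonstrated loss of power.

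**What to change.** - **Section 6.A.2:** add an exclusion for current use of ginseng-containing products, with the sponsor setting the look-back period.
- **Section 7.E:** have the sponsor state how non-study ginseng is handled in both arms during the 12 months.
- **Sections 7.D, 8 and 14:** name non-study ginseng and supplements in the existing co-administration question. Record use at baseline and at 1, 3, 6 and 12 months, with a form field and a line in the schedule.
- **Section 13:** report outside use by arm and keep intention-to-treat as the primary analysis.

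The cost is protocol wording and one form field, and a few current users would be screened out. Timing matters: this version is dated March 02, 2018 and section 5 ends the study on July 31, 2018, so patients due a 12-month visit by then would have been randomised by about the end of July 2017. The documents do not say whether enrolment is closed. If it is, the eligibility change comes too late, and only the recording at remaining visits and the reporting by arm still apply.

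### Primary outcome ii is judged by worsening of mRS, but the plan provides for no mRS rating before randomization

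*Combined protocol and SAP*

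**What the plan says.** Section 7.B gives two primary outcomes. The first is ischemic stroke or TIA by symptom history. The second is other cerebro-cardiovascular illness or death over one year, counted as a number of patients and assessed by "aggravation of patient status (mRS, modified Rankin Scale) at out-patient clinic during one-year follow-up".

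The only other mention of mRS is in the text under the Section 8 forms. Follow-up may be in clinic or by telephone, because "ischemic stroke or TIA history is asked, and mRS is evaluated in the interview". On timing, Section 7.D states: "Both groups will be followed up at 1, 3, 6 and 12 months after randomization". Section 14 gives the same four contacts, each with a window of ±2 weeks.

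The secondary flow outcomes are handled differently. One of them reads "Changes in velocity (cm/Sec) in quantitative MRA measured by percentage change from the baseline study", and Section 7.D bases these outcomes on "quantitative MR angiography studies performed at baseline and 12 months after randomization".

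The Section 8 form has event columns at 3, 6, 9 and 12 months. One of them is headed "The presence of any ischemic stroke history at 9 months follow-up".

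**The concern.** Worsening is a change, so it can be judged only against an earlier state. If the first mRS rating is made about a month after treatment starts, two errors become possible:

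- A patient who was already disabled at entry may be taken to have worsened, because nothing on file shows the earlier level.
- The month-1 rating may become the reference by default, so that non-fatal worsening in the first weeks is absorbed into it.

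Deaths, and worsening between later ratings, would still be visible. What is at stake is how reliably one of two listed primary outcomes is classified, in a trial planned for 29 patients per group. Analysts cannot create a missing starting value later unless patient records happen to hold it.

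**Working it through.** The plan states no figure for this point, so the check is a comparison of sections, followed by the direction of the error.

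**1. Where mRS is provided for**

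| Section | Content relevant to mRS |
|---|---|
| 7.B, primary outcome ii | Worsening of mRS is the means of assessment; no reference value and no amount of worsening given |
| 7.D | Outcome history, adverse effects, other drugs and compliance at 1, 3, 6 and 12 months; mRS not named; baseline named for MR only |
| 7.G | Evaluation of stroke and TIA by history and diffusion MRI; mRS not named |
| 8, form | No mRS field, at baseline or later |
| 8, follow-up text | mRS rated in the follow-up interview |
| 14 | Rows for consent, MR and drug compliance; the baseline column marks consent and MR only |

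No section provides for a rating before month 1. The form headings and schedule rows are legible, so damaged tables do not explain the gap.

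**2. Contrast with the secondary outcomes.** For flow and velocity, the baseline is part of the definition (7.B), and the baseline MR appears in 7.D, 7.H and Section 14. No such link exists for outcome ii.

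**3. Can patients enter with disability?** Section 6 sets no mRS limit and admits inpatients as well as outpatients. Stroke history is excluded only in part: "History of cardioembolic stroke or possibility of cardioembolic stroke". Earlier stroke of other ischemic types is not excluded as such. A further criterion, "History of previous intra-arterial thrombolysis, cerebral angioplasty and/or stenting, carotid endarterectomy, and bypass surgery", may remove some disabled patients, but not all.

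**4. Direction of the error.** Let p be the true event proportion in an arm, f the share of patients without an event who are counted as worse, and m the share of events missed. The observed proportion is

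p' = p(1 − m) + f(1 − p) = f + p(1 − m − f).

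If f and m are the same in both arms, the observed difference is (1 − m − f) times the true difference, which is a shrinkage toward zero. Randomization and blinding make equal shares the natural expectation, although chance imbalance in a small trial could move a single result either way. The documents give neither f nor m. The 0.1 and 0.4 in Section 7.C are stated for primary and secondary outcomes together, not for outcome ii. No size can therefore be derived.

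**5. Months on the form.** Contacts: {1, 3, 6, 12}. Event columns: {3, 6, 9, 12}. Months 3, 6 and 12 match. The 1-month contact has no column, and the 9-month column has no contact.

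**6. Time left.** This version is dated March 2, 2018, and Section 5 ends the study on July 31, 2018: 29 + 30 + 31 + 30 + 31 = 151 days. That is shorter than the 12-month follow-up. If the end date includes follow-up, all baseline visits had already taken place.

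**The case against.** **The outcome is not a bare mRS change.** Outcome ii requires cerebro-cardiovascular illness or death, and mRS is only the means of assessment. A patient with stable disability and no new vascular illness does not meet the text. This stands, and it limits false counts. It does not remove the problem, because an interviewer whose first rating is at month 1 has no recorded earlier level by which to tell stable from worse.

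**Section 7.G names only cerebral ischemic symptoms as the primary outcome.** Those are assessed by history and diffusion MRI and need no baseline mRS. This also stands, and it limits the consequence. Section 7.B nevertheless lists outcome ii as primary, so it needs a usable definition.

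**Section 7.D takes history of the primary outcome at each contact, including month 1.** Many early events would be caught this way. A reader might infer that every non-fatal event before month 1 is lost; the documents do not support that. What remains at risk is the judgment that a patient's status has worsened, which history alone does not fix.

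**The form and schedule are abbreviated.** Section 14 also omits stroke and TIA history and adverse effects, so silence there proves little by itself. Agreed; the point rests on the absence of a baseline rating in every section.

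**Routine records may hold an mRS.** Possibly, but nothing in the plan requires it.

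**Conclusion.** The gap is real and worth correcting, but moderate. As written, primary outcome ii has no pre-randomization reference for worsening. The likely direction is dilution, assuming similar error in both blinded arms. The size is unknown.

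A reader might go further and put a figure on lost power. The documents do not support that: they give no distribution of baseline disability, no misclassification rate and no event rates specific to outcome ii.

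A reader might also infer that the mismatch in months loses events. It need not. The columns record any stroke history, so a month-1 event can be entered at month 3, and a 12-month column exists for the one-year outcome. The mismatch is a clerical inconsistency that mainly affects timing.

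**What to change.** - Add a baseline mRS, and an mRS field at each contact, to Sections 8 and 14.
- Define the outcome ii event as death, or an mRS increase over baseline, attributed to a cerebro-cardiovascular cause other than the ischemic stroke or TIA already counted under outcome i. Counting any mRS increase would be too wide: it would take in non-vascular decline and count some strokes twice.
- For patients already enrolled, abstract the baseline score from existing records, blinded to arm and before unblinding. Report the source of each score and the number missing.
- Minor: reconcile the event columns in Section 8 (3, 6, 9, 12 months) with the contacts in Section 7.D and Section 14 (1, 3, 6, 12 months).

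The cost is one short score per patient and a form revision. If baseline visits are already over, only retrospective scores are possible. These are less reliable and may be missing for some patients, so the fix would narrow the gap without closing it.

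### Both QMRA secondary outcomes are defined as percentage change from baseline with no test or baseline adjustment named; a pre-stated baseline-adjusted analysis of the 12-month value is usually more efficient and needs no new data

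*Combined protocol and SAP*

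**What the plan says.** Section 7.B, secondary outcome i, is "Changes in volumetric blood flow (ml/Sec) in quantitative MRA measured", and the sentence goes on to the same percentage-change metric. Outcome ii is "Changes in velocity (cm/Sec) in quantitative MRA measured by percentage change from the baseline study".

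Section 7.D adds only that "The secondary outcomes will be evaluated by comparison of the results of quantitative MR angiography studies performed at baseline and 12 months after randomization". Section 7.H says "QMRA with NOVA will measure blood flow at the predetermined sites"; the sites are not listed, and no rule is given for choosing or combining them. Sections 7.H and 14 schedule the scan at baseline and at 12 months.

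Section 13 gives intention-to-treat and Fisher's exact test for the primary outcome. It names no test, model, covariate or transformation for QMRA.

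Section 7.C applies assumed proportions of 0.1 and 0.4 "in the analyses of primary and secondary outcomes, calculated sample size would be 29 patients each group".

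Entry (Section 6.A) requires "Severe stenosis or occlusion at an internal carotid artery, middle cerebral artery and vertebrobasilar system in cerebral angiography". Section 2 gives QMRA its purpose: "the changes of collateral perfusion state on an ischemic territory caused by atherosclerosis will be evaluated using" this scan as a surrogate. Section 7.H repeats it: "The results would become an indirect measurement of collateral flow state of a steno-occlusive vascular lesion".

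**The concern.** QMRA carries the mechanistic evidence of a small trial. Percentage change divides by a measured baseline, so baseline error enters the outcome, and a low reading can dominate an arm's mean. At zero baseline the outcome does not exist, and the plan has no rule for that. Because entry requires severe stenosis or occlusion, such readings are possible. The baseline scan is already paid for, and used as a covariate it would usually give a more precise comparison.

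At stake are power and readability for two secondary outcomes. Section 7.C's proportions do not describe a percentage change (they would suit outcome iii, new FLAIR lesions), so a dichotomised QMRA analysis is not excluded either.

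**Working it through.** **Inputs.** From the documents: 29 per group, alpha 0.05 (two-sided, from the equality test), power 0.8, scans at baseline and 12 months. Assumed: between-patient CV, baseline to 12-month correlation r, and effect.

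**1. The plan's own figure.** n = [0.1×0.9 + 0.4×0.6] × (1.960 + 0.842)² / 0.3² = 0.33 × 7.85 / 0.09 = 28.8, so 29. It reproduces, but for proportions; nothing was sized on QMRA.

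**2. Instability.** A rise of 0.3 ml/sec is 0.3/3.0 = 10% from a baseline of 3.0 and 0.3/0.1 = 300% from 0.1. From zero it is undefined.

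**3. Apparent rise with no true change.** For lognormal flow, mean percentage change = exp[s²(1−r)] − 1, with s² = ln(1 + CV²).
- CV 0.3, r 0.5: s² = 0.0862, giving 4.4%.
- CV 0.5, r 0.5: s² = 0.2231, giving 11.8%.

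Both arms shift equally, so the between-arm comparison is unbiased, but within-arm figures mislead.

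**4. Efficiency on the log scale.** Var(ANCOVA)/Var(change) = (1−r²)/[2(1−r)] = (1+r)/2, i.e. 0.75 at r 0.5 and 0.85 at r 0.7. Normal approximation for a 20% multiplicative effect (ln 1.2 = 0.182; √(2/29) = 0.263):
- r 0.5, CV 0.3 (s = 0.294). ANCOVA SE = 0.294 × √0.75 × 0.263 = 0.067, z = 2.73, power Φ(0.77) = 0.78. Change-score SE = 0.294 × 0.263 = 0.077, z = 2.36, power Φ(0.40) = 0.66.
- r 0.8, CV 0.5 (s = 0.472). ANCOVA SE = 0.472 × 0.6 × 0.263 = 0.074, z = 2.45, power 0.69. Change-score SE = 0.472 × √0.4 × 0.263 = 0.078, z = 2.32, power 0.64.

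**5. Simulated power** (29 per group, two-sided 5%; repeat runs agree to about 0.02):

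| Assumed setting | t-test on % change | Log ANCOVA |
|---|---|---|
| Multiplicative 20%: r 0.5, CV 0.3 | 0.62 | 0.76 |
| r 0.5, CV 0.5 | 0.28 | 0.38 |
| r 0.7, CV 0.5 | 0.43 | 0.51 |
| r 0.8, CV 0.5 | 0.62 | 0.67 |
| r 0.95, CV 0.5 | 0.994 | 0.995 |
| 5% low at baseline, follow-up varies: r 0.5, CV 0.3 | 0.31 | 0.69 |
| same, r 0.7, CV 0.5 | 0.26 | 0.49 |
| same, r 0.8, CV 0.5 | 0.32 | 0.60 |
| 20% stably low: r 0.5, CV 0.3 | 0.62 | 0.64 |
| same, r 0.7, CV 0.5 | 0.44 | 0.47 |
| same, r 0.8, CV 0.5 | 0.61 | 0.63 |
| Strictly proportional change, CV 0.5 | 0.85 | 0.83 |

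In the 5% rows, low patients start at 5–15% of typical flow and are at 5–50% at follow-up, so recovery is built in.

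**6. Adjustment versus scale.**
- Keeping percentage change as the outcome and adding baseline as covariate (log-SD 0.4, effect set for about 80% power of log ANCOVA) moved power from 0.64 to 0.73 at r 0.5, 0.71 to 0.76 at r 0.7, 0.76 to 0.78 at r 0.85, and left it at 0.79 at r 0.95. Adjustment itself never lost.
- Under an additive half-SD effect (CV 0.4), raw-scale against log ANCOVA is 0.58 vs 0.49 at r 0.5 and 0.74 vs 0.65 at r 0.7.
- With 20% low flows and additive scan error (SD 0.1), r 0.5: raw 0.58, log 0.42, percentage change 0.26.
- Raw can also lose: with multiplicative effects and log-SD 0.6, r 0.85, it has 0.67 against 0.79 for log and 0.74 for percentage change.

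**7. Zeros.** With 20% of sites at zero at both scans, percentage change / log ANCOVA in those with flow / rank ANCOVA in everyone: 0.53/0.66/0.56 (r 0.5, CV 0.3), 0.36/0.43/0.36 (r 0.7, CV 0.5), 0.51/0.56/0.48 (r 0.8, CV 0.5).

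**8. Type I error** over four null settings: 0.043–0.052 for the ANCOVAs; 0.028–0.049 for the percentage-change t-test.

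**The case against.** The plan names no QMRA test, so the unadjusted t-test is my comparator, not the sponsor's. A percentage-change metric does not forbid adjusting for baseline. This stands: adjustment is unspecified, not rejected, and the power losses are what would follow if the plain comparison were made.

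A reader might infer that occlusion at entry means very low or zero baseline flow, and so a large loss. The documents do not support that. The sites are unlisted and may be patent collateral vessels. Stable low flow costs percentage change almost nothing and shrinks the gain from adjustment; only low readings that are noisy or recover produce the large figures.

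A reader might also infer that the log scale is generally best. It is not, as the additive and scan-error results show.

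Finally, log ANCOVA drops patients whose flow is lost by 12 months, an exclusion after randomisation that sits badly with the intention-to-treat statement in Section 13. That stands too, and is why a rank-based analysis has to accompany it.

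**Conclusion.** The point holds as a low-cost improvement, at medium confidence. Percentage change is an inefficient metric with no rule for zero baseline, and the plan leaves its analysis open. Against an unadjusted t-test, log-scale ANCOVA gains roughly 0.05 to 0.14 in power at r 0.5 to 0.8 under multiplicative effects. The gain is far larger with a few erratic low flows, slight with stable low flows, nil at r 0.95, and about −0.02 under strict proportionality. All of these rest on assumed CVs, correlations and effects, so the benefit in this trial cannot be fixed. Baseline adjustment is the robust part; the best scale depends on how the effect acts.

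It would be wrong to read this as bias or excess false positives: the randomised comparison is unbiased, and simulated type I error stayed at about 5% or below. The primary result and the 29 per group are untouched.

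**What to change.** In Sections 7.B and 13, state that:

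- 12-month flow and 12-month velocity at the predetermined sites are each analysed by ANCOVA with treatment and the baseline value at the same sites, reported with a 95% CI.
- The site, or the rule for combining sites, is fixed before the 12-month scans are read.
- One scale is chosen before unblinding. Log gives a ratio readable as an adjusted percentage difference, closest to the present metric.
- Patients with zero or unmeasurable flow at either scan stay in a pre-stated rank-based ANCOVA (ranked 12-month value on ranked baseline), with zeros counted by arm and scan, and the plan says which analysis leads if the two disagree.
- Percentage change is kept as a descriptive summary where baseline is above zero.

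The cost is wording only, with no new data. The headline is slightly less simple, and about 0.02 of power is lost if change is strictly proportional. Very low values stay influential on the log scale, though less so: at r 0.5, CV 0.5, a move from 0.1 to 0.4 ml/sec is ln(4)/0.472 = 2.9 SD of log change, against (300 − 11.8)/55.9 = 5.2 SD of percentage change. With many stable zeros the rank-based result is only about level with percentage change.
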